9.5. Study Size

Since this is an exploratory study and no formal hypothesis-testing will be carried out, there is no formal sample size calculation. The sample size of this study depends on how many patients are eligible to participate in this observation and will agree to provide data for the questionnaire.

As of mid-July 2020, there were n = 202 pregnancy and pregnancy outcome reports for 184 female patients under SC Peginterferon beta-1a and n = 245 pregnancy and pregnancy outcome reports for 199 female patients treated with IM Interferon beta-1a in the MSSC database. The outcome of 368 pregnancies was a live birth, hence qualify for the prospective study part. About 290 patient questionnaires are expected to be completed during the telephone interview (80% return rate estimated). This number might increase until 15th October 2020 - the cut-off point for data collection.

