9.7. Data Analysis

This study is an observational study with focus on existing pregnancy reporting forms (retrospective part) and a patient's questionnaire which is completed at a single point of time (prospective part).

It will not be distinguished between the two treatments, i.e. the data will be pooled for analysis.

All documented data are analyzed by descriptive statistics, that is, no formal statistical hypothesis will be formulated, and no statistical tests will be carried out.

Categorical variables will be summarized descriptively by absolute frequencies and percentages. The denominator for all percentages will be the total number of pregnancies within the respective group, unless otherwise indicated. Percentages will be presented to one decimal place and will not be displayed for zero frequencies. A row denoted "Missing" will be included in all tabulations to clearly indicate the completeness of the collected data, i.e. missing data is included in the denominator of the percentages.

Continuous variables will be tabulated by descriptive statistics, i.e. the total number of pregnancies (n), number of pregnancies with missing values (Nmiss), mean, standard deviation, median, quartiles, minimum and maximum.

If sensible, free text entries will be transferred into appropriate encoding schemes to be analyzed in frequency tables. If appropriate, change of values during/after pregnancy to values before pregnancy will be calculated and analyzed using descriptive statistics or shift tables.

In case of missing or unknown data, no data imputation will be performed. For a complete presentation all obtained data will be listed.

A statistical analysis plan will be drafted and finalized before the end of the overall data collection to describe all analyses in more detail.

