9.7.1.2. Secondary Endpoint Analysis

The analysis set for the secondary objectives will be defined by the group of patients that gave written informed consent, had a live birth outcome, provided data for the patient questionnaire and were eligible to participate in this observation (see 9.2.1 **Fehler! Verweisquelle konnte nicht gefunden werden.**).

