9.9. Limitations of the Research Methods

The study will be non-comparative. The lack of an internal reference therapy is a weakness of this study and should be kept in mind when interpreting the data. In non-interventional studies, the amount of data cleaning is limited. Therefore, missing values and/or implausible values are to be expected. The SAP will provide a detailed description on how to handle those values. In general, no substitution of missing values is planned.

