The information contained herein may not be used, disclosed, or published without the written consent of Biogen MA Inc.

Section 7: Bias	Yes	No	N/A	Section Number
7.1 Does the protocol address ways to measure confounding? (e.g. confounding by indication)				
7.2 Does the protocol address selection bias? (e.g. healthy user/adherer bias)				
7.3 Does the protocol address information bias (e.g. misclassification of exposure and outcomes, time-related bias)				

Comments:

--

Section 8: Effect measure modification	Yes	No	N/A	Section Number
8.1 Does the protocol address effect modifiers? (e.g. collection of data on known effect modifiers, subgroup analyses, anticipated direction of effect)				

Comments:

--

Section 9: Data sources	Yes	No	N/A	Section Number
9.1 Does the protocol describe the data source(s) used in the study for the ascertainment of:				
9.1.1 Exposure? (e.g. pharmacy dispensing, general practice prescribing, claims data, self-report, face-to-face interview)				9.4.
9.1.2 Outcomes? (e.g. clinical records, laboratory markers or values, claims data, self-report, patient interview including scales and questionnaires, vital statistics)				9.4.
9.1.3 Covariates and other characteristics?				9.4.
9.2 Does the protocol describe the information available from the data source(s) on:				
9.2.1 Exposure? (e.g. date of dispensing, drug quantity, dose, number of days of supply prescription, daily dosage, prescriber)				9.4.
9.2.2 Outcomes? (e.g. date of occurrence, multiple event, severity measures related to event)				9.4.

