10.7 Does the plan describe methods for handling missing data?				9.7
10.8 Are relevant sensitivity analyses described?				

Comments:

PAS study with one pooled treatment

Section 11: Data management and quality control	Yes	No	N/A	Section Number
11.1 Does the protocol provide information on data storage? (e.g. software and IT environment, database maintenance and anti-fraud protection, archiving)				9.6
11.2 Are methods of quality assurance described?				9.6
11.3 Is there a system in place for independent review of study results?				9.8

CONFIDENTIAL

The information contained herein may not be used, disclosed, or published without the written consent of Biogen MA Inc.

Comments:

--

Section 12: Limitations	Yes	No	N/A	Section Number
12.1 Does the protocol discuss the impact on the study results of: 12.1.1 Selection bias? 12.1.2 Information bias? 12.1.3 Residual/unmeasured confounding? (e.g. anticipated direction and magnitude of such biases, validation sub-study, use of validation and external data, analytical methods)				9.9
				
				
12.2 Does the protocol discuss study feasibility? (e.g. study size, anticipated exposure uptake, duration of follow-up in a cohort study, patient recruitment, precision of the estimates)				9.2.3.1

Comments:

--

Section 13: Ethical/data protection issues	Yes	No	N/A	Section Number
13.1 Have requirements of Ethics Committee/ Institutional Review Board been described?				10.1
13.2 Has any outcome of an ethical review procedure been addressed?				10.1

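### The interview-only secondary results describe responding mothers alone; no comparison with non-responders is planned, and the protocol contradicts itself on whether it discusses selection bias

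*Protocol*

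**What the plan says.** Section 9.7.1.2 of the protocol defines the set for all secondary objectives as mothers who gave written consent, had a live birth, "provided data for the patient questionnaire and were eligible to participate in this observation". Sections 9.2.3.1 and 10.2 set the route in: a telephone approach, a consent form sent by mail and returned signed, and then the interview. Under section 9.2.3.3, a consented mother who cannot be reached gets no questionnaire.

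Section 9.5 gives the expected yield: "The outcome of 368 pregnancies was a live birth, hence qualify for the prospective study part", followed by "About 290 patient questionnaires are expected to be completed during the telephone interview (80% return rate estimated". The abstract expects about 310.

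Annex 2 asks, in item 7.2, "Does the protocol address selection bias? (e.g. healthy user/adherer bias" and the box ticked is N/A. Item 12.1 asks "Does the protocol discuss the impact on the study results of: 12.1.1 Selection bias" and the box ticked is Yes, with section 9.9 as the reference. Item 10.8, on sensitivity analyses, is ticked No. Section 9.9 itself says that "The lack of an internal reference therapy is a weakness of this study" and then turns to limited data cleaning and to missing or implausible values. It says nothing about selection or non-response.

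**The concern.** Several steps separate an eligible mother from a completed questionnaire, and each is voluntary. Willingness to take part could plausibly depend on the child's health, the mother's MS course or the time since birth. These are close to what the interview measures. The results at stake are child development up to 48 months and maternal relapses, the parts of the study that the rationale in section 7.2 presents as new.

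A reader of the final report would see proportions among responders. The planned row for missing values does not help, because section 9.7 counts it within the group being analysed and non-responders are not in that group. The protocol's account of its limitations does not warn the reader either, although the checklist says that it does.

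**Working it through.** **Inputs**
- Live-birth pregnancies that qualify: 368 (section 9.5, mid-July 2020).
- Return rate: "80% return rate estimated" (section 9.5).
- Expected questionnaires: about 290 (section 9.5) and about 310 (abstract).

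**The plan's own figure.** 368 × 0.80 = 294.4. The stated 290 agrees within 1.5%. The abstract's 310 does not follow from the same inputs: 310 / 368 = 84.2%, or, at 80%, 310 / 0.80 = 387.5 live births.

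**Live-birth pregnancies outside the secondary set, out of 368**
- At 80%: 368 − 294 = 74 (20.1%).
- At 290 questionnaires: 368 − 290 = 78 (21.2%).
- At 310 questionnaires: 368 − 310 = 58 (15.8%).

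The 80% is applied to pregnancies, although it is mothers who respond. The 447 reports (202 + 245) come from 383 women (184 + 199). If that ratio carries over, which is an assumption, 368 live births belong to about 368 × 383 / 447 = 315 women.

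**What this can do to a proportion.** With response fraction f, the rate for all live births is f × p(responders) + (1 − f) × p(non-responders). The protocol gives no event rate, so the 10% and the multiples below are assumptions for illustration.
- Non-responders at half the rate: 0.80 × 10% + 0.20 × 5% = 9%.
- Non-responders at double the rate: 0.80 × 10% + 0.20 × 20% = 12%.
- Limits if none or all of the 74 are affected: 294 / 368 × 10% = 8.0%, and 8.0% + 20.1% = 28.1%.

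The width between the limits is simply the non-response fraction: about 20 percentage points at 80% return, and 16 to 21 over the document's figures.

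**What is available on non-responders.** Eligibility (section 9.2.1) requires both pregnancy reports, and a live birth must already be recorded for the interview part. Live-birth status and basic exposure are therefore known. The planned extract (section 9.4.1) also lists malformation status, gestation week, newborn measurements, maternal age and interferon use. Sections 9.2 and 9.2.3.1 allow its use under the programme's privacy policy, without the study consent form.

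There is one limit. Section 9.4.2 says that gaps in the reports are filled during the interview, and section 9.6 feeds the completed forms back into the database. Responders' records will therefore become more complete than non-responders' records, so a fair comparison needs the values as they stood before the interviews.

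**What such a table could show.** With 294 against 74, the standard error of a standardised difference is √(1/294 + 1/74) = 0.13. Differences of about 1.96 × 0.13 = 0.25 standard deviations or more would stand out; smaller ones might not.

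**The case against.** The strongest reply is that this is a matter for the SAP. Section 9.7 promises an SAP with more detail, the study is descriptive ("no formal statistical hypothesis will be formulated, and no statistical tests will be carried out"), and restricting interview endpoints to those interviewed is unavoidable. Ticks of N/A or No in the checklist record what the protocol contains; they do not forbid a later table. Much of this stands, and the missing table alone would not be a finding. What the SAP cannot repair is the protocol's claim, in item 12.1.1, that section 9.9 discusses selection bias. Moreover, section 9.9 leaves to the SAP only missing and implausible values, not mothers outside the analysis set.

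Some stronger readings are tempting, and the documents do not support them:
- **Full data exist for every non-responder.** Section 9.4.1 lists fields to be extracted and does not say that they are complete; section 9.4.2 expects gaps.
- **The database information on non-responders goes unused, or they have no child data at all.** The primary set in section 9.7.1.1 does not depend on the interview, so malformations and preterm births are reported for all eligible pregnancies. Non-responders lack only the interview data.
- **The secondary results must be reweighted for non-response.** Later child health and MS activity are unobserved in non-responders, so weights built on birth-time variables correct only for what is recorded. With about 74 non-responders and incomplete predictors, the response model would also be fragile.
- **Return may be far below 80%.** The protocol states no other rate.

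**Conclusion.** The point holds as a gap in what can be concluded, together with a contradiction in the text. About 74 of 368 live-birth pregnancies (20%; 58 to 78 across the document's figures) are expected to have no interview data. No comparison with them is planned, and the protocol answers the selection-bias question in two incompatible ways.

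A reader might infer that the 48-month child results are biased. The documents do not show that: neither the presence nor the direction of bias can be known from them. The shift from 10% to 9% or 12% rests wholly on assumed rates and shows only the order of size. The counts rest on the mid-July 2020 database and the 80% estimate, and section 9.5 says that numbers may rise by the cut-off. The primary endpoints are not affected.

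**What to change.** - In section 9.7.1.2, add a descriptive table of responders against non-responders among all eligible live births: malformation status, gestation week and preterm birth, birth weight, maternal age, product and interferon history. Use database values as extracted before interview completion, and show completeness per field. No test is needed, so the descriptive design is kept.
- State the number of non-responders beside each interview-only result.
- In section 9.9, name non-response as a limitation.
- Reconcile checklist items 7.2 and 12.1.1 with each other and with section 9.9.
- Reconcile the 290 in section 9.5 with the 310 in the abstract, so that the expected non-response is one figure.
- Treat weighting for non-response as an optional supplement at most.

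The cost is one extra table from data already being extracted, a copy of the extract frozen before the interviews, and a few sentences of text. The downside is that some fields will be incomplete for non-responders, which the completeness column makes visible.

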9.7.2. Subgroup Analysis

Subgroup analyses will be performed with respect to patient's interferon beta-1a treatment history before during and after pregnancy. The primary endpoint will be evaluated in following subgroups:

- SC Peginterferon beta-1a or IM Interferon beta-1a was taken continuously before and during pregnancy
- SC Peginterferon beta-1a or IM Interferon beta-1a therapy was paused/stopped during pregnancy
- SC Peginterferon beta-1a or IM Interferon beta-1a therapy was started during pregnancy

The secondary endpoints will be evaluated in following subgroups:

- SC Peginterferon beta-1a or IM Interferon beta-1a was taken continuously before, during and after the pregnancy
- SC Peginterferon beta-1a or IM Interferon beta-1a therapy was started during pregnancy
- SC Peginterferon beta-1a or IM Interferon beta-1a therapy was paused during pregnancy and restarted promptly (within 1 week) after "life birth"
- SC Peginterferon beta-1a or IM Interferon beta-1a therapy was stopped during pregnancy and restarted more than a week after "life birth"
- SC Peginterferon beta-1a or IM Interferon beta-1a therapy was stopped during pregnancy and not restarted after "life birth"

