Research Question and Objectives:	
This study's main research question is to assess the course of pregnancy and infant outcomes in pregnant women with MS from Biogen's German MS Service-Center Database.
 
Primary Objective: The primary objective(s) of the study is to evaluate the impact of exposure to SC Peginterferon beta-1a or IM Interferon beta-1a before and during pregnancy on pregnancy outcome in female patients who had registered in the German PSP and of whom a pregnancy report and pregnancy outcome report is available.
 
Secondary Objectives: The secondary objectives of this study are applicable for a subpopulation of the above-mentioned population, i.e. for patients of whom data on a standardized questionnaire collected during a telephone interview is available. The secondary endpoints are as follows:
 
 • Average birth weight, average birth length, and head circumference of the newborn • To evaluate the impact of exposure to SC Peginterferon beta-1a or IM Interferon beta-1a before and during pregnancy on child development up to 48 months of age • To assess the SC Peginterferon beta-1a or IM Interferon beta-1a treatment behavior for pregnant women or women becoming pregnant in daily real life • To assess the other MS treatment behavior during/after pregnancy • To assess the use of certain concomitant medications (i.e. non-disease-modifying therapies) taken during pregnancy • To evaluate the effect of SC Peginterferon beta-1a or IM Interferon beta-1a exposure before, during, and after pregnancy on MS disease activity • To assess the effect of breastfeeding under SC Peginterferon beta-1a or IM Interferon beta-1a therapy on the MS disease activity • To assess the benefit of exclusive breastfeeding versus complementary feeding on the MS disease activity in women breastfeeding under SC Peginterferon beta-1a or IM Interferon beta-1a therapy

CONFIDENTIAL

The information contained herein may not be used, disclosed, or published without the written consent of Biogen MA Inc.

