7. RATIONALE AND BACKGROUND

Multiple sclerosis (MS) is the most common autoimmune disease of the central nervous system, mainly affecting women of reproductive age [Hauser and Oksenberg, 2006], with pregnancy and birth outcomes being major concerns for many women with MS. The PRIMS study (Pregnancy in Multiple Sclerosis multicenter European study) showed that, overall, pregnancy did not affect the long-term clinical course of MS [Vukusic 2004]. PRIMS provided evidence that relapse rates go down during pregnancy in MS women, and then restart after giving birth. The study also showed that disability progression is similar between pregnant MS women and the general MS population, suggesting that the overall impact of pregnancy on MS course seems to be neutral [Houtchens et al., 2018; Vukusic 2004].

There is a lack of safety information on drug's use in pregnancy as clinical trials rarely include pregnant women. As a consequence, most information regarding the safety/risk profile of drugs during pregnancy is collected after the drug has been approved and used by pregnant women intentionally or unintentionally.

More than 20 years of experience is available on the use of interferon beta treatment to treat multiple sclerosis [Hegen 2015, O'Connor 2014], and their safety and efficacy in MS therapy have been established, even with long-term use.

Interferon beta-1a once weekly was approved by the European Medicines Agency (EMA) in 1997 and has a well know safety and tolerability profile, with a long-term experience of more than 23 years. The products risk-benefit ratio has remained positive in the long-term treatment.

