8. RESEARCH QUESTION AND OBJECTIVES

8.1. Research Question

This study’s main research question is to assess the course of pregnancy and infant outcomes in pregnant women with MS from Biogen’s German MS Service-Center Database.

Another aim is to learn more about if/when in real life SC Peginterferon beta-1a or IM Interferon beta-1a therapy is stopped for women who become pregnant in the real life setting and if/when the interferon-beta therapy is continued postpartum.

Furthermore, it will be assessed if there is a difference in the MS disease progression depending on the interferon beta exposure and breast-feeding practices.

Data of women exposed to SC Peginterferon beta-1a and IM Interferon beta-1a prior to the pregnancy, during the pregnancy and postpartum will be evaluated for course of pregnancy and pregnancy outcome.

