9.1.2. Secondary Endpoints

- Average weight, average length, and average head circumference of the children from birth to 48 months
- Number and proportion of abnormalities diagnosed during pediatric check-ups under statutory programs in Germany and reported in the standardized German pediatric check-up booklet “Kinderuntersuchungsheft” (data on check-ups 1-8 will be collected covering the first 46 - 48 months of life). Refer to Annex 3 for recommended timepoints and details on the examinations.
- Number and proportion of women discontinuing SC Peginterferon beta-1a or IM Interferon beta-1a therapy during pregnancy and time to discontinuation in relation to beginning of pregnancy

CONFIDENTIAL

The information contained herein may not be used, disclosed, or published without the written consent of Biogen MA Inc.

- Number and proportion of women starting SC Peginterferon beta-1a or IM Interferon beta-1a therapy during pregnancy and time to start in relation to beginning of pregnancy
- Number and proportion of women restarting SC Peginterferon beta-1a or IM Interferon beta-1a therapy after birth and time to restart in relation to birth
- Number and proportion of women starting another MS therapy during/after pregnancy and time to start in relation to birth
- Number and proportion of women using other therapies during pregnancy (categorized by Paracetamol, other therapies for the alleviation of FLS), folic acid, medication for depression, corticosteroids, adrenocorticotrophic hormone, other therapies)
- Number and proportion of MS relapses in women with SC Peginterferon beta-1a or IM Interferon beta-1a therapy before, during and after pregnancy
- Change of EDSS during and after pregnancy to EDSS before pregnancy
- Lactation: number of women breastfeeding under SC Peginterferon beta-1a or IM Interferon beta-1a therapy and duration of SC Peginterferon beta-1a or IM Interferon beta-1a exposed breastfeeding
- Time to first MS relapse after introduction of the first supplemental feedings in women with SC Peginterferon beta-1a or IM Interferon beta-1a therapy during lactation

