9.4.2. Prospective Data Capture

If the pregnancy report or the pregnancy outcome report is incomplete, i.e. the data above was not collected, the open questions will be addressed during a telephone interview performed by the MSSC and the new information will be entered into the MSSC database. No further assessments other than completion of the questionnaire are applicable for patients participating in the prospective study part. The patient questionnaire is completed at a single point of time during the telephone interview performed by the MSSC.

The patient questionnaire covers the following questions:

- Abnormalities diagnosed during pediatric check-ups under statutory programs as reported in the standardized German pediatric check-up booklet “Kinderuntersuchungsheft” (data on check-ups 1-8 will be collected covering the first 46-48 months of life)
- Pregnancy and family anamnesis
- Vitamin K prophylaxis
- Body weight, height, head circumference of the child as documented for check-ups 2-8.
- Lactation:
 - Exclusive breastfeeding and duration (1st week, 1 month, 2 months, 3 months, 5 months, 6 months, 7-9 months, 10-12 months, > 12 months) of breastfeeding
 - Supplemental feedings (starting month after birth)
- Other MS therapies (non-interferon beta-1a DMTs) during or after pregnancy and start relative to birth (during pregnancy, < 1 week after birth, after 1 week, after 2 weeks, after 3 weeks, after 4 weeks, after 6 weeks, after 2 months, after 3 months, after 4 months, after 5 months, after 6 months, after 7 months, after 8 months, after 9 months, after 10 months, after 1 months, after 12 months or later))
- Frequency of MS relapses in the year before pregnancy
- Time (1st trimester, 2nd trimester, 3rd trimester) and frequency of MS relapses during pregnancy

CONFIDENTIAL

The information contained herein may not be used, disclosed, or published without the written consent of Biogen MA Inc.

- Time (< 1st month, 1st – 2nd month, 3rd - 4th month, 5th - 6th month, 7th - 8th month, 9th - 10th month, 11th - 12th month, 13th - 14th month, 15th - 16th month, 17th - 18th month, > 18th months) and frequency of MS relapses after pregnancy/birth
- EDSS before, during and after pregnancy

The information collected by the MSSC will be stored in a secure database.

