9.2.3 Covariates and other characteristics? (e.g. age, sex, clinical and drug use history, co-morbidity, co-medications, lifestyle)				9.4.
9.3 Is a coding system described for:				

CONFIDENTIAL

The information contained herein may not be used, disclosed, or published without the written consent of Biogen MA Inc.

Section 9: Data sources	Yes	No	N/A	Section Number
9.3.1 Exposure? (e.g. WHO Drug Dictionary, Anatomical Therapeutic Chemical (ATC) Classification System)				9.7
9.3.2 Outcomes? (e.g. International Classification of Diseases (ICD), Medical Dictionary for Regulatory Activities (MedDRA))				CRF
9.3.3 Covariates and other characteristics?				9.7
9.4 Is a linkage method between data sources described? (e.g. based on a unique identifier or other)				

Comments:

Exposure of study drug does not need any coding, other medication and free text entries will be categorized in analysis programs and outcomes of children are already categorized in the standardized German pediatric check-up booklet.

Section 10: Analysis plan	Yes	No	N/A	Section Number
10.1 Are the statistical methods and the reason for their choice described?				9.5, 9.7
10.2 Is study size and/or statistical precision estimated?				9.5
10.3 Are descriptive analyses included?				9.7
10.4 Are stratified analyses included?				
10.5 Does the plan describe methods for analytic control of confounding?				
10.6 Does the plan describe methods for analytic control of outcome misclassification?				

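### Relapse and EDSS results by interferon treatment history are not stratified by or adjusted for prior-year relapses, so they cannot support the stated aim of an exposure effect

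*Protocol*

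**What the plan says.** The abstract lists as a secondary objective "To evaluate the effect of SC Peginterferon beta-1a or IM Interferon beta-1a exposure before, during, and after pregnancy on MS disease activity", and section 8.3 repeats it. Section 8.1 adds that "it will be assessed if there is a difference in the MS disease progression depending on the interferon beta exposure and breast-feeding practices".

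Section 9.7.2 supplies the breakdown by exposure: "Subgroup analyses will be performed with respect to patient's interferon beta-1a treatment history before during and after pregnancy". For the endpoints at issue here it states: "The secondary endpoints will be evaluated in following subgroups". There are five groups:

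- interferon continued throughout
- started during pregnancy
- paused and restarted within one week of birth
- stopped and restarted more than a week after birth
- stopped and not restarted

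The relapse endpoint in section 9.1.2 is "Number and proportion of MS relapses in women with SC Peginterferon beta-1a or IM Interferon beta-1a therapy before, during and after pregnancy". EDSS is analysed as change from the pre-pregnancy value. The questionnaire in section 9.4.2 records "Frequency of MS relapses in the year before pregnancy".

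Section 9.7 plans descriptive statistics without tests. It foresees changes from pre-pregnancy values or shift tables where appropriate. Section 9.9 calls the study non-comparative. The limitations it names are the missing reference therapy and limited data cleaning.

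In Annex 2, item 10.5 ("Does the plan describe methods for analytic control of confounding") is answered No. So are item 10.4 (stratified analyses) and item 7.1 (ways to measure confounding). Item 12.1.3 is ticked Yes, as if section 9.9 discussed residual confounding.

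**The concern.** The study is non-interventional, so women and their physicians decide whether interferon is continued, paused, restarted or dropped. Such decisions plausibly depend on disease activity before pregnancy, which also predicts later relapses. If women with more active disease continue or restart early, interferon will look ineffective or harmful after birth. If women with milder disease stay on it, interferon will look protective.

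The variable that would show and partly correct this is already collected. As planned, it appears as one row of the relapse endpoint. Separate rows for relapses before and after pregnancy give two marginal distributions per subgroup. They do not show whether women with the same prior relapse history fared differently under different treatment histories.

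A simple before/after comparison within each woman does not fill the gap. Section 7 itself says that "relapse rates go down during pregnancy in MS women, and then restart after giving birth", so pregnancy alone changes the relapse rate.

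**Working it through.** **1. The base for these tables.** Section 9.5 gives 368 live-birth pregnancies and an 80% return rate: 368 × 0.80 = 294.4, which reproduces its figure of about 290. On an even split (an assumption), 290 / 5 = 58 per subgroup, and with two prior-relapse strata 290 / (5 × 2) = 29 per cell. The abstract expects about 310 questionnaires, which would give 31 per cell and change nothing here.

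**2. What the tables contain.** Sections 9.1.2 and 9.7.2 together put pre-pregnancy relapses into the subgroup tables, and EDSS is taken relative to baseline. No section crosses later relapses or EDSS change with the prior-year relapse count. Section 9.7.3 tabulates age, weight, height and history, but does not list prior relapses.

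**3. How large the distortion could be.** The documents give no relapse risk by subgroup or by prior relapse, so every input in this step is assumed. The drug effect is set to zero. Let r0 and r1 be the post-partum relapse risk without and with a prior-year relapse, and p the share of a subgroup with such a relapse.

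Crude subgroup risk = r0 + (r1 − r0) × p

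Crude difference between subgroups A and B = (r1 − r0) × (pA − pB)

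| r0 / r1 | pA 30%, pB 30% | 40%, 30% | 50%, 30% | 60%, 20% |
|---|---|---|---|---|
| 20% / 30% | 0 | 1 | 2 | 4 |
| 20% / 40% | 0 | 2 | 4 | 8 |
| 15% / 45% | 0 | 3 | 6 | 12 |

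Entries are percentage points. Example: (0.45 − 0.15) × (0.60 − 0.20) = 0.12. The non-zero entries correspond to crude risk ratios of 1.04 (24% vs 23%) to 1.57 (33% vs 21%). Within each prior-relapse stratum the difference is 0 by construction.

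**4. Sampling error for scale.** At an assumed 30% risk, the 95% half-width for a difference between two groups of 58 is 1.96 × √(2 × 0.3 × 0.7 / 58) = 0.167, about 17 points. With 30 per group it is about 23 points.

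**The case against.** **Pre-pregnancy data are not ignored.** A reader might infer that the prior relapse count goes unused. The documents do not support that: the relapse endpoint includes the period before pregnancy and is shown by subgroup, and EDSS is a change from baseline. A reader of the tables could see an imbalance. This stands, and it limits the point to the missing stratification or adjustment.

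**Changes could be compared across subgroups.** A pregnancy pattern common to all subgroups would cancel in such a comparison. That is fair, and section 7 rules out only the simple before/after reading. But change tables are conditional in section 9.7, and no comparison of changes between subgroups is specified. It would also need the pattern to be the same at every level of prior activity.

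**The study is descriptive and non-comparative.** No between-group estimate or test is planned, so any harm lies in interpretation. This stands as to where the harm arises. It does not remove the conflict with objectives worded as an effect and a difference.

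**Cross-tabulations belong in the SAP.** Table detail does, and the SAP is not shown. But Annex 2 answers No to stratified analyses and to control of confounding, which are stated choices. Section 9.9 leaves to the SAP only the handling of missing and implausible values.

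**Sampling error exceeds the bias.** On the assumptions above, about 17 points against at most 12. True, but random error does not cancel a systematic one, and imprecision is a further reason not to claim an effect.

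**One binary stratifier is weak.** This stands. Pre-pregnancy EDSS, age and other influences on treatment choice remain. Three of the five subgroups are defined by whether and when treatment was restarted after birth, so a post-partum relapse could itself prompt a restart. Stratifying on prior relapses cannot remove that.

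**Conclusion.** The concern holds in a limited form. Relapse and EDSS results are to be shown by subgroups that treatment decisions create, without stratification or adjustment for a collected baseline measure of disease activity. Such tables cannot answer a question about the effect of exposure. The Annex 2 answers make this a stated choice, and the tick at item 12.1.3 conflicts with section 9.9, which does not mention confounding.

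Two stronger readings are not supported. One is that the subgroups do differ in background disease activity; this is plausible, but the documents hold no data on it. The other is that a bias of known size exists. The 1 to 12 points rest entirely on assumed risks and shares, with no drug effect, and the figure is 0 if the shares are equal.

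Only secondary objectives are affected; the pregnancy-outcome endpoints are untouched. The protocol should be changed, because the remedy uses data already collected.

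**What to change.** - **Section 9.7.2:** tabulate relapses and EDSS change, during and after pregnancy, by treatment-history subgroup within 0 and at least 1 relapse in the year before pregnancy, where cell size allows. Show the prior-year relapse distribution per subgroup beside these tables.
- **Section 9.9:** name confounding by indication. State also that the restart groups are defined by events after birth, so a post-partum relapse may have led to the restart. This makes the tick at Annex 2 item 12.1.3 true.
- **Annex 2:** change item 10.4 to Yes. Describe item 10.5 as partial at most, since one stratifier does not amount to control of confounding.
- **Sections 4, 8.1 and 8.3:** word the disease-activity objectives, including those on breastfeeding, as descriptive associations. This is needed even with stratification, which reduces confounding but does not remove it. No table of relapse by feeding practice is specified, so for feeding the change is to the wording only.

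The cost is protocol and SAP wording and a few more tables, with no new data and no tests. The downside is small cells: about 29 on an even split, fewer in practice for some groups. The group that started interferon during pregnancy may be too small to stratify.
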